## 17.0 APPENDIX B

### Adverse Event Guidance Document

#### General Statement

As any new investigational product may have unexpected adverse events, the following guidance is offered for potential, but unexpected, toxicities for HM15211. The following diagnostic work-up and procedures are suggested actions and should be tailored to the clinical presentation as assessed by the Investigator.

#### 1. Cardiovascular Toxicity

##### Definitions:

*Signs and symptoms may include:*

chest pain, arrhythmia, palpitations, peripheral edema, progressive or acute dyspnea, pleural effusion, fatigue

##### Diagnostic Workup:

At baseline:

- Electrocardiogram
- Cardiac biomarkers (creatinine kinase and troponin)

Depending on presentation:

- Inflammatory biomarkers (ESR, CRP, WBC count)
- O2 Saturation
- BNP
- Emergency room/hospital transfer
- Cardiology consultation
- Chest x-ray

Additional testing to be guided by cardiology and may include:

- Echocardiography
- Stress test
- Cardiac catheterization
- Cardiac MRI

| Grading*  | Management  |
|---|---|
| G1: Asymptomatic abnormal cardiac biomarker testing, including abnormal ECG  | 
All grades warrant workup and intervention given potential for cardiac compromise
 
Please consider the following:
 
 
Hold therapy and permanently discontinue after G1
 
  |
| G2: Mild symptoms consistent with cardiotoxicity with or without abnormal cardiac biomarkers   | 
 
Management of cardiac symptoms according to ACC/AHA guidelines
 
Transfer patient to the emergency room at the hospital for further evaluation and management for any grade > G1
 
Cardiology consultation
 
 |
| G3: Moderate symptoms consistent with cardiotoxicity and/or clinically significant abnormal cardiac biomarkers   |   |
| G4: Moderate to severe decompensation, intravenous medication or intervention required, life threatening conditions  |   |
| 
Qualifying Statement: Treatment recommendations are based on local standards of care and the life- threatening nature of cardiovascular complications. Holding therapy is recommended for complication grades greater than G2. The appropriateness of rechallenging remains unknown.
 |   |

\* Not associated with CTCAE grading system

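### The cardiovascular toxicity table in Appendix B gives study-drug thresholds that do not agree at G2 (minor; advisory text)

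*Protocol*

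**What the plan says.** Section 17.0 (Appendix B), part 1, Cardiovascular Toxicity, contains one table with four grades, G1 to G4. G1 is an abnormal biomarker or ECG without symptoms. G2 is defined as "Mild symptoms consistent with cardiotoxicity with or without abnormal cardiac biomarkers".

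The management column is introduced with "Please consider the following". Its study-drug bullet is "Hold therapy and permanently discontinue after G1". A later bullet reads "Transfer patient to the emergency room at the hospital for further evaluation and management for any grade" above G1, and a further one adds cardiology consultation.

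The qualifying statement at the foot of the table says: "Holding therapy is recommended for complication grades greater than G2". It then adds: "The appropriateness of rechallenging remains unknown".

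On the standing of the appendix, its General Statement says: "The following diagnostic work-up and procedures are suggested actions and should be tailored to the clinical presentation as assessed by the Investigator". The body of the protocol is worded more firmly. Section 4.2 says that cardiac events will be handled under this plan, and section 10.5 says the same of drug-related adverse events.

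**The concern.** The column and the qualifying statement draw the line for acting on study drug in different places: above G1 in one, above G2 in the other. G2 lies between the two lines.

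This is stop-drug advice for a cardiac event class that the protocol singles out in advance, in a trial with weekly dosing at up to 8 sites. Two investigators who each follow the table could treat the same G2 subject differently. One would stop the drug. The other could note that a hold is recommended only from G3 and give the next weekly dose. What is at stake is consistent handling of subjects. No estimate or error rate is involved.

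**Working it through.** No arithmetic applies, because the protocol states no figure on this point and makes no formal sample size calculation. The check sets the statements of the one table side by side, grade by grade.

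| Grade | Column: study drug (to consider) | Column: emergency room | Qualifying statement |
|---|---|---|---|
| G1 | hold, on the most natural reading | not advised | no hold recommended |
| G2 | permanent discontinuation | advised | no hold recommended |
| G3, G4 | permanent discontinuation | advised | hold recommended |

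1. **G3 and G4.** Both sentences call for action on study drug. The remark on rechallenge fits a subject whose drug is on hold and has little bearing on one who has been permanently stopped.

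2. **G1.** The column raises a hold at most, and only for consideration. The qualifying statement is silent. This is compatible with investigator discretion and is not the problem.

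3. **G2.** The column raises permanent discontinuation, and the emergency room bullet applies. The qualifying statement does not reach this grade, since G2 is not greater than G2. Here the two sentences part.

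4. **Reading of the column.** The words after G1 could mean grades above G1 or following a G1 event. On either meaning a G2 subject is not spared. I take the bullets as one cell covering all grades, because the column opens by saying that every grade warrants work-up and intervention. The row boundaries in the extracted table are uncertain, so this is an assumption.

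5. **Does another section settle it?** Section 6.4.4 leaves discontinuation for an adverse event to the investigator. Section 7.4 bars check-in for a medical condition judged to interfere with the study. Section 8.4 requires medical monitor approval to continue after a dose missed by more than 1 day. None of these names a grade, so they limit the consequence without saying which threshold prevails.

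6. **Does anything downstream depend on it?** The stopping rules in section 6.4.2 do not use these grades. They mention CTCAE as an optional scale, and the table's footnote says its own grading is not CTCAE. No endpoint in section 5 is defined by them.

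7. **How many subjects?** The protocol gives no rate for G1 or G2 cardiac events. Section 4.3 reports no cardiac adverse events so far in the single-dose study.

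**The case against.** The strongest defence is that the two sentences differ in force. The column lists things to consider, and the qualifying statement recommends. Read as a ladder, an investigator may hold or stop the drug at lower grades, and from G3 a hold becomes the firm minimum. The skin table in the same appendix works this way, with a hold to be considered at G2 and directed at G3. The label of the closing sentence also suggests that it qualifies the column above it. And the appendix openly invites investigators to tailor its advice, so some variation between them is intended.

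Much of this stands. On the ladder reading there is no strict contradiction, and the advisory status keeps the point small. The remark on rechallenge can be taken as a general caveat about missing evidence.

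Two things do not go away. The ladder is nowhere stated in the cardiovascular table; the skin table writes it out row by row, and here the reader must infer it. And if the qualifying statement is taken to govern, the table sends a G2 subject to the emergency room for suspected cardiac toxicity without recommending that the drug be held meanwhile.

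A reader might go further and infer that the order of the actions is inverted, with permanent discontinuation starting at a lower grade than a hold. The text does not support that. The column's own bullet names a hold together with discontinuation, so within the column a hold comes no later. The inversion appears only if a considered discontinuation is set against a recommended hold and the column's hold is left out.

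**Conclusion.** The table is wrong as written, but in a minor way: the hold threshold in the qualifying statement does not match the emergency transfer and discontinuation thresholds in the column, and G2 is where this shows. It is an inconsistency in wording, not a firm reversal of the order of actions.

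The practical risk is limited. Emergency room transfer and cardiology consultation are advised at G2 whichever sentence is followed, so giving another dose would be a supervised clinical decision. The number of subjects concerned cannot be estimated from the protocol and may be zero. No conclusion about safety, pharmacokinetics or liver fat depends on the point.

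The verdict rests on reading the management bullets as applying to all grades and on the absence of any rule elsewhere that ranks the two sentences. Which cut is clinically right is not a question that the document answers.

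**What to change.** Align the hold with the cut above G1 that the table already uses for emergency transfer. In the qualifying statement, replace the sentence on holding with: *A hold on study drug is recommended at G2 and above (any grade greater than G1), pending cardiology work-up; permanent discontinuation should be considered.* Limit the rechallenge sentence to subjects who have not been permanently discontinued. Leave G1 to the investigator's discretion.

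Two other repairs are tempting: recommending a hold already at G1, or raising the column to G3. Each would take a clinical position that the text does not settle, so neither is proposed.

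The cost is a small wording change in the next amendment, with no change to data collection or sample size. The downside is possibly a few more held doses in mildly symptomatic subjects, because the listed signs are broad: "chest pain, arrhythmia, palpitations, peripheral edema, progressive or acute dyspnea, pleural effusion, fatigue". Each held dose is 1 of 12 weekly doses (1/12 = 8.3%) for that subject, and a dose missed by more than 1 day brings in the medical monitor under section 8.4. If a hold ended in discontinuation, one active subject is 1 of 9 in a dose group (1/9 = 11.1%), although section 6.1 allows replacement.

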## 2. Rash/Inflammatory Dermatitis and Other Skin Disorders

### Definitions:

- Erythema multiforme major and minor (a targetoid reaction in the skin and mucous membranes usually triggered by infections, such as Herpes Simplex Viruses, but can be associated with an immune-related drug eruption and if progresses to EM major, it can be a harbinger of SCAR, such as SJS)
- Lichenoid (resembling the flat-topped, polygonal and sometimes scaly or hypertrophic lesions of lichen planus)
- Eczematous (Inflammatory dermatitis characterized by pruritic, erythematous, scaly or crusted papules or plaques on the skin, which is vulnerable to superinfection)
- Psoriasiform (resembling the well-demarcated, erythematous and scaly papules and plaques of psoriasis)
- Morbilliform (a non-pustular, non-bullous measles-like exanthematous rash of the skin often referred to as “maculopapular” and without systemic symptoms or lab abnormalities, excluding occasional isolated peripheral eosinophilia)
- Palmoplantar erythrodysaesthesia (PPE) (hand-foot syndrome) (redness, numbness/burning/itching and superficial desquamation of the palms and soles)
- Neutrophilic dermatoses (e.g. sweet's syndrome)
- Others

### Diagnostic Workup for Skin Disorders above and Others Considered to be Possibly IP-related:

- Pertinent history and physical exam
- Rule out any other etiology of the skin problem, such as an infection, an effect of another drug or a skin condition linked to another systemic disease or unrelated primary skin disorder
- If needed, a biological checkup including a blood cell count, liver and kidney tests
- Directed serologic studies if an autoimmune condition is suspected, such as lupus or dermatomyositis: a screening antinuclear antibody test, SSA/Anti-Ro, SS-B/Anti-La if predominantly photodistributed/photosensitivity, anti-histone, ds-DNA and other relevant serologies. Consider expanding serologic studies or diagnostic work up if other autoimmune conditions are considered based on signs, symptoms.
- Dermatology consultation with skin biopsy
- Consider clinical monitoring with use of serial clinical photography, if IRB approved and subject has consented

- Review full list of patient medications to rule out other drug-induced cause for photosensitivity

| Grading   | Management  |
|---|---|
| 
Grading according to CTCAE criteria is a challenge for skin. Instead, severity may be based on BSA, tolerability, morbidity, and duration.
 |   |
| 
G1: Symptoms do not affect the quality of life or controlled with topical regimen and/or oral antipruritic
                          | 
 
• Consider continuing therapy for mild localized reaction, e.g., injection site erythema
 
• Consider treatment with topical emollients and/or mild-moderate potency topical corticosteroids
 
• Counsel patients to avoid skin irritants and sun exposure
 
  |
| 
G2: Inflammatory reaction that affects quality of life and requires intervention based on diagnosis.
                                | 
 
• Dermatology consultation with possible biopsy
 
• Consider holding therapy and monitor weekly for improvement. If not resolved, interrupt treatment until skin AE has reverted to grade 1
 
• Consider initiating prednisone (or equivalent) at dosing 1 mg/kg tapering over at 4 weeks
 
 
In addition, treat with topical emollients, oral antihistamines and medium-to-high potency topical corticosteroids
 |
| 
G3: As grade 2 but with failure to respond to indicated interventions for a grade 2 dermatitis.
                                     | 
 
• Hold therapy and consult with dermatology to determine appropriateness of resuming
 
• Treat with topical emollients, oral antihistamines and high potency topical corticosteroids
 
• Initiate oral prednisone or equivalent (0.5-1 mg/kg/day) tapering over at least 4 weeks
 
  |

|  |  |
|--|--|
| 
G4: All severe rashes not manageable with prior intervention
 | 

• Immediate hold therapy and consult dermatology to determine appropriateness of resuming therapy upon resolution of skin toxicity and once corticosteroids are reduced to prednisone (or equivalent) 10mg or less.

• Systemic steroids: IV (methyl)prednisolone (or equivalent) dosed at 1–2mg/kg with slow tapering when the toxicity resolves

• Monitor closely for progression to Severe Cutaneous Adverse Reaction

• Should admit patient immediately with an urgent consult by dermatology

 |
|--|--|

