### 7.2 Exclusion Criteria

Subjects who meet any of the following criteria will be excluded from the study:

1. Subjects with a history of or active chronic liver disease due to alcohol, autoimmune, HIV, HBV or active HCV-infection or NASH disease.
2. Any history of clinically significant chronic liver disease including esophageal varices, ascites, encephalopathy or any hospitalization for treatment of chronic liver disease; or Model for End Stage Liver Disease (MELD)  $\geq 10$ .
3. Previous surgical treatment for obesity (bariatric surgery, gastric banding, etc.) or any other gastrointestinal surgery that may induce malabsorption, history of bowel resection  $> 20 \text{ cm}$ , any malabsorption disorder, severe gastroparesis, any GI procedure for weight loss (including LAP-BAND®), as well as clinically significant gastrointestinal disorders (e.g. peptic ulcers, severe gastrointestinal reflux disease [GERD]) at Screening.

4. Pacemaker, implanted electronic devices, metal fragments, aneurysm clips in the brain that could interfere with the MRI examination.
5. Use of any prohibited concomitant medication (as listed in the table Prohibited Medication below) from time points specified until completion of the study.
6. Uncontrolled hypertension, defined as systolic blood pressure  $>150$  mmHg and/or diastolic blood pressure  $\geq 100$  mmHg at screening (reading may be repeated on a different day). (Subjects with uncontrolled hypertension may be rescreened after 3 months, following initiation or adjustment of antihypertensive therapy).
7. Any weight control treatment within 3 months prior to Screening.
8. Participation in an investigational study within 30 days prior to dosing or 5 half-lives within the last dose of investigational product whichever is longer.
9. Personal history or current diagnosis of acute or chronic pancreatitis or factors for pancreatitis, such as a history of cholelithiasis (without cholecystectomy) or alcohol abuse.
10. History of major depression, anxiety, suicidal behavior or attempts, or other psychiatric disorder (within 2 years of screening), requiring medical treatment, including selective serotonin reuptake inhibitors (SSRIs), serotonin norepinephrine reuptake inhibitors (SNRIs), antipsychotics, lithium.
11. History of any major surgery within 6 months prior to screening.
12. History of any serious adverse reaction or hypersensitivity to study drugs components.

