### 7.3 Prohibited Medications

Use of the agents listed in [Table 7-1](#) (prescription or nonprescription) is prohibited from the time points specified until completion of all study activities.

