**Table 7-1 Prohibited Medications**

| Medication or Class  | Indication/Reason  | From time point specified until the end of the study                    |
|--|--|---|
| Antihypertensive medication  | Hypertension   | Excluded unless on stable dose for at least 3 months prior to screening |
| Statins  | Hyperlipidemia   | Excluded unless on stable dose for at least 3 months prior to screening |
| Oral or systemic long-acting corticosteroids   | Eg, chronic or acute non-infectious inflammatory conditions, autoimmune diseases                     | Within 3 months prior to screening                                      |
| Antacids, anticholinergics, antispasmodics (eg, modafinil, phenytoin), 5HT3 antagonists, dopamine antagonists, or opiates, antiemetics                           | Reduction/modification of GI motility  | Within 2 weeks prior to screening                                       |
| Orlistat, lorcaserin, sibutramine, etc., including over-the-counter and herbal supplements, or any medication with a labelled indication for weight loss or gain | Weight control treatment   | Within 3 months prior to screening.                                     |
| Any anti-diabetic medication   | Diabetes   | Any prior treatment   |
| Selective serotonin reuptake inhibitors (SSRIs), serotonin norepinephrine reuptake inhibitors (SNRIs), antipsychotics, lithium.                                  | Depression, anxiety, psychiatric disorders   | Current treatment   |
| Use of SSRIs and SNRIs (including bupropion)   | For reasons other than active psychiatric indications (eg, migraine, weight loss, smoking cessation) | Within 3-month prior to screening.                                      |

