**Severity of symptoms should be assessed as following:**

| Grading
(Not associated with CTCAE grading system)                                  | Management   |
|--|--|
| G1: Mild symptoms that do not interfere with quality of life                    | 

• No intervention

  |
| G2: Mild to moderate symptoms that may need intervention based on Investigator. | 

• Patient observation

• Consider initiating antiemetic medication

  |
| G3: Moderate to severe symptoms that need medical intervention.                 | 

• Hold therapy; resume therapy only if symptoms are fully resolved

• Treat with antiemetic medication as indicated

• Treat with IV fluid

• Treat with parenteral nutrition if no oral intake sustained beyond 7 days

 |
| G4: Life-threatening symptoms   | 

• Immediately discontinue therapy

• Systemic IV fluids

• Treat with antiemetic medication as indicated

• Treat with parenteral nutrition

• Should admit patient immediately with an urgent consult

           |

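### The protocol bans antiemetics to study end with no exception for treating adverse events, yet Appendix B tells sites to use them; systemic steroids may have the same conflict

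*Protocol*

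**What the plan says.** **The ban.** Section 7.3 states that use of the agents in Table 7-1 is barred in these terms: "prescription or nonprescription) is prohibited from the time points specified until completion of all study activities". One row of the table lists "5HT3 antagonists, dopamine antagonists, or opiates, antiemetics", for their effect on gastrointestinal motility. Another lists "Oral or systemic long-acting corticosteroids". Exclusion 5 repeats the ban: "Use of any prohibited concomitant medication (as listed in the table Prohibited Medication below) from time points specified until completion of the study". The only exceptions in the table are for antihypertensives and statins at a stable dose. Section 2.0 carries a copy of the table.

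**Check-in.** Section 7.4 item 4 applies at in-patient periods and outpatient visits. It refuses check-in after any medicine, other than allowed concomitant medication, in the previous 24 hours. Section 9.1.12 item 4 sets the same bar for the two in-house periods with a 12-hour window. Neither defines what is allowed.

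**The contrary instruction.** Section 10.5 says drug-related adverse events will be managed under Appendix B.
- Appendix B section 4 (gastrointestinal): at G2, "Consider initiating antiemetic medication", with no hold of study drug; at G3 and G4, antiemetic treatment as indicated.
- Appendix B section 2 (skin): at G2, "Consider initiating prednisone (or equivalent) at dosing 1 mg/kg tapering over at 4 weeks"; at G3, "Initiate oral prednisone or equivalent (0.5-1 mg/kg/day) tapering over at least 4 weeks"; at G4, intravenous steroids. At G4 dermatology is also asked to "determine appropriateness of resuming therapy upon resolution of skin toxicity and once corticosteroids are reduced to prednisone (or equivalent) 10mg or less".

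**The concern.** A site has to follow both texts, and for antiemetics they cannot both be followed. Nausea and vomiting are the events most likely to raise the question. Section 4.3 names them as the main drug-related events in the single-dose study, and Appendix B calls them anticipated.

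One site may treat at G2 and keep dosing, as Appendix B suggests. Another may withhold the antiemetic because of Table 7-1, or give it and then refuse the subject at the next weekly visit. The same clinical course can thus end as a dose given, a dose missed or a recorded deviation.

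Deviation status has consequences. Section 6.4.4 provides for withdrawal when a violation may interfere with the pharmacokinetics or pharmacodynamics. The PK and PD sets (12.2.1.2, 12.2.1.3) leave out subjects with major deviations that affect those measures, and the PD set serves the MRI-PDFF endpoint.

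**Working it through.** The plan has no figure to reproduce. The check sets the texts side by side and looks for a sentence that reconciles them.

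**1. Which Appendix B rows name a listed agent** (oral or systemic agents only)

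| Appendix B row | Agent | In Table 7-1? |
|---|---|---|
| GI G1 | none | – |
| GI G2 | antiemetic, to be considered; no hold | yes, outright |
| GI G3 | antiemetic; study drug held | yes, outright |
| GI G4 | antiemetic; study drug discontinued | yes, outright |
| Skin G1 | none systemic | – |
| Skin G2 | prednisone, to be considered | depends on 'long-acting' |
| Skin G3 | oral prednisone; study drug held | depends on 'long-acting' |
| Skin G4 | intravenous steroid; study drug held | depends on 'long-acting' |

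Gastrointestinal: 3 of 4 rows, unconditional. Skin: 3 of 4 rows, conditional. Together 3 + 3 = 6 of 8 rows, of which 3 are certain.

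**2. What happens at check-in.** Take a subject with GI G2 vomiting who is given an antiemetic less than 24 hours before a weekly visit. Appendix B states no hold, so the dose is due. Under 7.4 item 4 the subject is turned away unless the antiemetic is allowed, and Table 7-1 prohibits it expressly. If the medicine was taken between 12 and 24 hours before the Day 77 admission, 7.4 refuses the subject and 9.1.12 item 4 does not. Section 7.4 permits one rescheduling; 9.1.12 permits two and then excludes the subject.

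**3. Steroids.** Two questions decide this part. The first is whether 'long-acting' qualifies oral agents as well as systemic ones, and if so whether prednisone is long-acting; the protocol does not say. The second is whether prednisone is an allowed medicine under 7.4. At skin G4 the restart limit of 10 mg or less includes 0 mg. At 0 mg, with the last dose outside the window, both texts are satisfied. Above 0 mg and up to 10 mg, daily prednisone falls within 24 hours of every visit and meets the bar unless it counts as allowed.

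**4. Where an exception might sit.**
- Section 10.4.1 requires appropriate treatment of adverse events at the investigator's discretion. It does not mention Table 7-1 or check-in.
- Section 9.1.7 has medication changes recorded at each visit and the sponsor informed if eligibility to continue is affected. It grants no permission.
- Section 8.4 requires medical monitor approval after a dose is missed by more than a day. It does not waive 7.4.
- Section 6.4.4 leaves withdrawal to judgment. It does not say that the medicine is permitted.

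None of these lifts the ban.

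**The case against.** The strongest defence is that adverse event treatment is implicitly allowed. The check-in rules except allowed medication without defining it, 10.4.1 requires subjects to be treated, 10.5 points to Appendix B, and Appendix B calls its contents suggestions to be tailored to the patient. For prednisone this is a fair reading, and it is why that part is conditional. For antiemetics it asks the reader to presume that an agent prohibited by name is allowed. A suggestion to use a prohibited medicine still conflicts with the prohibition.

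Three stronger readings are tempting, and the documents do not support them.
- *A G4 restart on prednisone is impossible.* A reader might infer this from 7.4. It does not follow: 'allowed' is undefined, and a restart at 0 mg meets both texts. No drug-related skin event had been noted in the single-dose study, so this part is also contingent.
- *Antiemetic use would shift the escalation decision.* Emesis is the primary tolerability criterion (6.4.1), so a reader might infer an effect on the count. Nothing in the protocol shows one or its size. Severe emesis includes any case requiring intravenous fluids, and Appendix B prescribes these at GI G3 and G4, so such cases count as severe regardless of antiemetic use. Any effect would lie mainly at G2.
- *The 10 mg limit is missing from skin G2 and G3.* G2 has its own restart condition (return to grade 1), and G3 leaves resumption to dermatology. A limit stated only at the highest grade is not a contradiction.

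One caution stands. The ban has a reason, the effect of these agents on gut motility, so an exception should not settle whether a treated subject's PK or PD data are usable.

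**Conclusion.** The contradiction is established for antiemetics: prohibited by name to study end, called for in 3 of 4 gastrointestinal grades, with no reconciling sentence. Read literally, the protocol refuses dosing to, or records a deviation for, a subject managed as it directs for an anticipated event. For systemic steroids the same conflict is possible in 3 of 4 skin grades, subject to the two questions of reading above.

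The size is a count of protocol rows. How many subjects would be affected cannot be derived, because the protocol gives no incidence. The conclusion assumes only that 'allowed' does not silently include an agent listed as prohibited. The point should be corrected; it does not undermine the design.

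**What to change.** Add to 7.3, and as a footnote to Table 7-1 and its copy in Section 2.0, wording such as: *Medication started on study to treat an adverse event under Appendix B, including antiemetics and systemic corticosteroids, is an allowed concomitant medication. Its use is not by itself a protocol deviation or a reason for withdrawal.* Refer to it in exclusion 5, 7.4 item 4 and 9.1.12 item 4.

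Keep the Appendix B holds, the dermatology decision at skin G3 and G4, and medical monitor approval under 8.4. Leave PK and PD set membership to the existing definitions in 12.2.1.2 and 12.2.1.3.

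The cost is two sentences, a footnote in two places, three cross-references and a note to sites. Visits, sample size and data collection are unchanged. The downside is that antiemetic use stays discretionary and may differ between sites. It should therefore be shown next to the emesis data at each escalation review; it is already recorded under 9.1.7.
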